### b. Secondary Outcomes

- i. Rate of images per total fractions (outcome as continuous variable)
  - 1. Change in rate of images per total fractions taken pre and post intervention in each arm
- ii. Multivariate analysis for factors associated with reduction in daily IGRT
  - 1. Cohort (intervention vs. control arms)
  - 2. Age
  - 3. Sex
  - 4. Race
  - 5. ECOG
  - 6. Insurance type (Commercial, Medicare , Medicaid, Uninsured, Unknown)
  - 7. Target type (Brain, bone, soft tissue, multiple sites, other)
  - 8. Prior radiation (course 1 vs. not course 1)
  - 9. Total number of fractions per course
  - 10. Dose per fraction
    - a. [name] will send us a distribution of this data and we will bucket it accordingly.
  - 11. Attending
  - 12. Time of day
  - 13. Location (PCAM vs. satellite)
- c. Exploratory Analyses
  - i. Change in treatment time (in minutes)
    - 1. Change in total treatment time between pre- and post-intervention periods in each arm
  - ii. Cost analysis
    - 1. Change in cost before and after intervention implemented in each arm
      - Use CPT codes (charges) and Medicare standardized reimbursements to determine change in healthcare costs pre and post default intervention

Analysis Plan – Reducing Daily Palliative IGRT

Commented [SS1]: Insurance status is from the Epic output as follows: Unknown, Blue Shield, Commercial, Managed Care, Managed Medicaid, Managed Medicare, Medicaid, Medicare, Self pay. These can probably be further consolidated - Perhaps: unknown, self pay, (Blue shield+commercial+managed care), (Managed Medicaid+Medicaid), (Managed medicare+medicare).

3

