Overuse of IGRT is particularly apparent during palliative radiation treatments. Our department has demonstrated that for the palliative treatment of brain metastases standard, clinical immobilization and setup techniques without the use of daily IGRT are sufficient for treatment in routine cases. Moreover, evidence-based guidelines clearly state that "IGRT generally is not medically necessary in the palliative setting." Yet despite uncertain clinical need and decreasing reimbursements, physicians often reflexively order daily imaging for treatment.

4.3. Preliminary data. At our institution, across the University of Pennsylvania Health System (UPHS) Radiation Oncology network, 79% of palliative intent radiation courses over the past year (August 2015 – August 2016) utilized daily x-ray image guidance as part of the treatment paradigm. As shown in Table 1, despite clinical guidelines recommending against the use of daily IGRT in palliative cases, 83% of bone metastases, 82% of soft tissue metastases, and 57% of palliative brain/ CNS cases employed daily IGRT during the associated radiation treatment course.

Palliative Type	Total N	% Courses w Daily IGRT
Bone	459	83.4%
Brain/ CNS	133	57.1%
Soft Tissue	216	82.4%
Unknown	2	50.0%
SBRT	21	100.0%

Table 1: Use of Daily IGRT in Palliative Cases at UPHS by Treatment Indication

\*Daily IGRT defined as at least 80% (i.e., 4 of 5 days, on average) of treated fractions in a treatment course have IGRT

\*\*SBRT: Stereotactic Body Radiation Therapy

As shown in Table 2, the total number of palliative courses and associated daily IGRT varies across our main site and satellites. Our main site, the Perelman Center for Advanced Medicine (PCAM), has the highest volume of cases overall, and, hence, the highest number of palliative courses. All sites across the UPHS radiation oncology network, however, demonstrate high levels of daily IGRT usage in palliative courses. Over the past year, the number of palliative courses treated at each department was roughly stable over time as shown in Table 3, other than a slight rise in the number of cases treated during the month of June.

[figure not shown]
Location	Total N	% Courses w Daily IGRT
PCAM	623	81.4%
PAH	56	58.9%
СНН	39	79.5%
DH	55	76.4%
VF	52	80.8%
Unknown	6	66.7%
Grand Total	831	79.3%

**Table 2:** Use of Daily IGRT in Palliative Cases by UPHS Radiation Oncology Department

 Location

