## 9. Analysis plan

The primary analysis will use a mixed effects logistic regression model, where the unit of analysis is an individual patient, the outcome is use of daily x-ray imaging and the explanatory variables are time (pre-intervention vs. post-intervention period), dummy variable for whether the intervention is received, group (PCAM vs. satellite providers) and physician random effects. The coefficient of interest is the coefficient of whether the intervention is received. The physician random effects account for the clustering by physician. The study is analyzed at the physician level (patients clustered within physicians) rather than the practices site level because there are only two practice sites. Of the two practice sites – PCAM vs. non-PCAM sites – one group will be assigned to the intervention for the entire intervention period by coin flip, and the other group of providers will be assigned to the control for the first two months of the intervention. Randomly assigning the order of practice sites exposed to the intervention helps to blunt selection bias. For this analysis, we have 89% power to detect an effect of the intervention that reduces the probability of daily imaging by 0.2 for each physician.

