# 4. Outcome measures

- a. Primary Outcome
  - i. Change in daily IGRT use from baseline pre-intervention period to intervention periods within the control and intervention arms
    - 1. Daily IGRT defined as at least 80% (i.e., 4 of 5 days, on average) of treated fractions in a treatment course have image guidance
  - ii. Change in daily IGRT use between control and intervention arms during first intervention period (3/10/17-6/9/17)

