# 2. Unadjusted Analysis

- a. Daily IGRT
  - i. Calculate daily IGRT use during pre-intervention period (2/10/16-2/9/17)
    1. Display graphically by month and cohort (PCAM vs. satellites)
  - ii. Calculate daily IGRT use at PCAM and satellites after intervention implemented (2/10/17-10/10/17)
    - 1. Display graphically by month and cohort (PCAM vs. satellite)
    - 2. Indicate on graph when intervention occurred at PCAM (2/10/17) and satellites (6/10/17)
  - iii. Conduct statistical analysis of change in daily IGRT pre and post intervention with 95% CI and p values
    - 1. Change in daily IGRT use from baseline pre-intervention period to intervention periods in both the control and intervention arms
      - Intervention group: Pre-intervention period (2/10/16-2/9/17) use of daily IGRT vs. Post-intervention period (3/10-17-10/10/17) use of daily IGRT
      - Control group: Pre-intervention period (2/10/16-6/9/17) use of daily IGRT vs. Post-intervention period (7/10-17-10/10/17) use of daily IGRT
    - Change in daily IGRT use during first intervention period (3/10/17-6/9/17) between usual care group (control) and intervention arms

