#### b. Primary model + relevant patient level factors

- 1. Intervention
  - 2. Attending (clustering at level of attending)
  - 3. Location
  - 4. Time?
  - 5. Age
  - 6. ECOG
  - 7. Prior radiation
  - 8. Insurance type (Commercial, Medicare , Medicaid, Uninsured, Unknown)
  - 9. Total number of fractions per course
- c. Sensitivity model
  - i. Covariates:
    - 1. Cohort (intervention vs. control arms)
    - 2. Age
    - 3. Sex
    - 4. Race
    - 5. ECOG
    - 6. Insurance type (Commercial, Medicare , Medicaid, Uninsured, Unknown)
    - 7. Target type (Brain, bone, soft tissue, multiple sites, other)
    - 8. Prior radiation (course 1 vs. not course 1)
    - 9. Total number of fractions per course

Commented [SS6]: Time defined as days from intervention?

- 10. Dose per fraction
- 11. Attending
- 12. Time of day
- 13. Location (PCAM vs. satellite)
- d. Assess missing data
- e. Unadjusted and adjusted analyses for covariates in relation to primary outcome (daily IGRT use)

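### SAP 4.b.ii asks which factors go with a reduction in daily IGRT, but no planned model has a term that could show it

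*SAP*

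**What the plan says.** SAP Study Overview 4.b.ii names the item "Multivariate analysis for factors associated with reduction in daily IGRT". Thirteen covariates follow, the first being "Cohort (intervention vs. control arms" and the last "Location (PCAM vs. satellite". No link function, analysis population or model terms are given. The list has no indicator for whether a course was exposed to the default, and no time term.

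The same 13 items reappear as the sensitivity model in Analysis Plan 3.c. Item 3.e then calls for "Unadjusted and adjusted analyses for covariates in relation to primary outcome (daily IGRT use".

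The outcome is one yes/no value per course: "Daily IGRT defined as at least 80% (i.e., 4 of 5 days, on average) of treated fractions in a treatment course have image guidance". Protocol section 9 describes the primary model as one "where the unit of analysis is an individual patient".

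Intervention and time appear only in the primary model (3.a) and its extension with patient factors (3.b), each as a single term. The SAP Methods paragraph describes a logit GEE clustered by attending, with month and site as covariates.

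**The concern.** A single course has no reduction; it either met the 80% rule or did not. A reduction exists only as a contrast between unexposed and exposed courses. To say that a factor is associated with reduction, that contrast must be compared across the levels of the factor. This needs a product term or an equivalent stratified estimate, and neither is written down for any patient or course factor.

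If the 13 items are fitted as main effects, each coefficient compares the level of daily IGRT between subgroups, averaged over courses before and after the default. Factors with low use before the default existed would then be reported as factors associated with reduction. The table could also point the wrong way about where the default worked, and that is what a department extending the default would want to know.

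**Working it through.** **1. Search for a term that could carry the answer.**

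| Place | Exposure to default | Time | Factor × intervention or period |
|---|---|---|---|
| Protocol section 9 | single dummy | pre/post | none |
| SAP 4.b.ii (13 items) | none | none | none |
| SAP 3.a, primary model | single term | single term | none |
| SAP 3.b, plus patient factors | single term | single term, marked as a query | none |
| SAP 3.c (same 13 items) | none | none | none |
| SAP Methods | intervention contrast reported | month | none |

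**2. Baseline level difference.** Protocol 4.3 reports that "83% of bone metastases, 82% of soft tissue metastases, and 57% of palliative brain/ CNS cases employed daily IGRT". Table 1 gives bone 83.4% (459 courses) and brain/CNS 57.1% (133 courses).

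OR, brain vs bone = (0.571/0.429) / (0.834/0.166) = 1.331 / 5.024 = 0.265, with no default in place.

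**3. Crude pooling over periods.** Assume 12 pre and 7 post months and even volume, so pooled use = (12 × pre + 7 × post)/19.

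- Both fall 20 points: bone (12 × 0.834 + 7 × 0.634)/19 = 0.760; brain (12 × 0.571 + 7 × 0.371)/19 = 0.497; OR = 0.31.
- Bone falls 30 points, brain 5: bone (12 × 0.834 + 7 × 0.534)/19 = 0.723; brain (12 × 0.571 + 7 × 0.521)/19 = 0.553; OR = 0.47.

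In the second case the drop is six times larger in bone, yet brain still shows the lower odds.

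**4. Would adding exposure as a main effect repair it?** Logistic models were fitted to expected counts (Table 1 volumes, post period 7/12 of a year, no clustering), without and with a target-by-default product term.

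| Assumed effect of default | Brain vs bone OR, main effects plus exposure | Ratio of default ORs (brain/bone) from product term |
|---|---|---|
| None | 0.26 | 1.00 |
| Log odds lowered by 1 in both | 0.26 | 1.00 |
| 20 points in both | 0.29 | 1.29 |
| 25 points in bone only | 0.45 | 3.58 |
| 35 points in brain only | 0.15 | 0.21 |

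The main-effect OR is below 1 in all five rows, and it is the same when the default does nothing as when it lowers the odds equally. The product term separates the cases. The third row shows that the scale matters: an equal 20-point drop is an OR of (0.634/0.366)/5.024 = 0.345 in bone and (0.371/0.629)/1.331 = 0.443 in brain, a ratio of 1.29.

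**5. Precision of an interaction.** Let bone fall 20 points (to 63.4%) and brain fall less by d. The variance of the difference in reductions is the sum of p(1−p)/n over four cells, with n = 459, 459 × 7/12, 133 and 133 × 7/12. The SE is about 0.079. Assuming a two-sided 0.05 test and no clustering, power is about 24% for d = 10 points, 48% for 15 and 72% for 20. True power would be lower, because courses cluster by physician and the satellites have only 3 post months.

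**6. Cohort and Location.** SAP 2.a.i says "Display graphically by month and cohort (PCAM vs. satellites", and the study arms section makes PCAM the intervention arm and the four satellites the control arm. Items 1 and 13 are therefore one variable and cannot both be estimated.

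**The case against.** The strongest reply is that the SAP never states a main-effects model. Item 4.b.ii is a bare list, and nothing says that 3.c or 3.e implements it. The Methods paragraph describes sensitivity analyses as the main model with patient characteristics added, so 3.c may be only an adjustment set for the intervention effect. Item 3.e refers to the primary outcome, which SAP 4.a words as a change, although its parenthesis names use. All of this stands, and it is why the main-effects reading is an inference. It does not close the gap: if change was meant, some term must carry it, and none is written.

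Second, reduction by arm is already planned. SAP 2.a.iii and 2.b compare pre with post separately in PCAM and the satellites. That is correct, but those comparisons are unadjusted and cover that one factor only.

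Third, the illustration has limits. Table 1 is not shown to exclude IMRT, proton or same-site retreatment courses. The 12/7 split is PCAM's; SAP 2.a.iii gives the satellites 16 pre and 3 post months. The 30/5 scenario is hypothetical. A reader might also take Pennsylvania Hospital against PCAM as a larger example, but the listed contrast is PCAM against all satellites. Those pool in Table 2 to about 148/202 = 73.3%, against 81.4% at PCAM, giving a baseline OR of about 0.63.

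Fourth, interactions here have low power. That argues for few of them with an exploratory label, and does not justify reporting level differences as reduction.

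**Conclusion.** The point holds as a mismatch between the title of a secondary outcome and everything the plan specifies to deliver it. On the natural reading, the analysis would identify who receives daily IGRT. The size is illustrative: a brain versus bone OR of about 0.26 before any default, and about 0.47 after a drop that strongly favours bone, under the Table 1 rates and 12/7 months with even volume.

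A reader might infer more: that the SAP prescribes a main-effects model, that a study objective goes unanswered, or that the trial's main result is compromised. The documents do not support these. No model form is given for 4.b.ii, the item is listed as a secondary outcome while the SAP's single stated objective is to reduce daily imaging, and the primary analysis does not depend on this item.

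**What to change.** In SAP 4.b.ii:

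- Use the main model (intervention exposure, month, site, clustering by attending). Add a factor and its product with intervention, one factor at a time, for a small pre-specified set of patient or course factors such as target type, prior radiation and insurance. Do not do this for Attending, which has about 29 levels and is already the clustering unit.
- Name one scale. The adjusted percentage-point reduction within each level, and the difference between levels, is preferable, with confidence intervals from the physician-level bootstrap already in the Methods.
- Label these results exploratory, and state that power is low and that there is no multiplicity control.
- Drop either Cohort or Location.
- Retitle any main-effects table as factors associated with daily IGRT use, and make 3.e consistent with it. Restricting the list to post-default courses is no substitute, since it shows who still gets daily IGRT.

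The cost is SAP wording and a few extra model runs on data already collected, with wider intervals than a main-effects table would show.

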#### 1. Descriptive Analysis

- a. Calculate the data for Table 1. Variables listed below
  - i. Cohort (intervention vs. control arms)
  - ii. Age
  - iii. Sex
  - iv. Race
  - v. ECOG
  - vi. Insurance type (Commercial, Medicare , Medicaid, Uninsured, Unknown)
  - vii. Target type (Brain, bone, soft tissue, other)
  - viii. Prior radiation (course 1 vs. not course 1)
  - ix. Total number of fractions per course (median with interquartile range)
  - x. Total dose (median with interquartile range; followed by buckets)
  - xi. Dose per fraction (median with interquartile range; followed by buckets)
  - xii. Time of day

# 2. Unadjusted Analysis

- a. Daily IGRT
  - i. Calculate daily IGRT use during pre-intervention period (2/10/16-2/9/17)
    1. Display graphically by month and cohort (PCAM vs. satellites)
  - ii. Calculate daily IGRT use at PCAM and satellites after intervention implemented (2/10/17-10/10/17)
    - 1. Display graphically by month and cohort (PCAM vs. satellite)
    - 2. Indicate on graph when intervention occurred at PCAM (2/10/17) and satellites (6/10/17)
  - iii. Conduct statistical analysis of change in daily IGRT pre and post intervention with 95% CI and p values
    - 1. Change in daily IGRT use from baseline pre-intervention period to intervention periods in both the control and intervention arms
      - Intervention group: Pre-intervention period (2/10/16-2/9/17) use of daily IGRT vs. Post-intervention period (3/10-17-10/10/17) use of daily IGRT
      - Control group: Pre-intervention period (2/10/16-6/9/17) use of daily IGRT vs. Post-intervention period (7/10-17-10/10/17) use of daily IGRT
    - Change in daily IGRT use during first intervention period (3/10/17-6/9/17) between usual care group (control) and intervention arms

#### b. Rate of images per total fractions (outcome as continuous variable)

- i. Change in rate of images per total fractions taken pre and post intervention in each arm with 95% CI and p values
  - 1. Calculate this separately for PCAM vs. satellites
    - a. PCAM: pre intervention (2/10/16-2/9/17) vs. post intervention (3/10/17-10/10/17)
    - Satellites: pre intervention (2/10/16-6/9/17) vs. post intervention (7/10/17-10/10/17)

Commented [DMG2]: Would make cohort columns to compare populations

Should look like this for example:				
	PCAM		Satellite	
	Pre	Post	Pre	Post
Race				
Age				

**Commented [SS3]:** Excludes the 1 month roll out period (2/10/17-3/9/17)

JB: Make sure [name] agrees \*\*

10/15/17 Update: [name] agrees that we should exclude roll out month

**Commented [SS4]:** Does preintervention period for control group end 2/9/17 or 6/9/17?

Need to confirm w [name]\*\*

10/15/17 Update: [name] says preintervention period ends 6/9/17 for satellites

**Commented [SS5]:** Excludes 1 month roll out (6/10/17-7/9/17)

SS: Confirm with [name]\*\*

10/15/17 Update: [name] agrees that we should exclude roll out month

 Change in rate of images per total fractions between PCAM (intervention group) and satellites (control group) during first intervention period (3/10/17-6/9/17)

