### c. Treatment time

- i. We have 3 times recorded for each patient at the level of each fraction
  - 1. Activity time
    - This is the time until treatment start (while patient is being set up for treatment), and is the window during which IGRT would be acquired
    - b. We will need to account for small percentage (~4%) of missing data in activity time
  - 2. Treatment start (won't really use this)
  - 3. Treatment end
- ii. Create variable to calculate "total treatment time" (treatment end activity time start)
  - 1. Total treatment time = activity (set up) time + treatment time
- iii. Following comparisons needed with 95% CI and p values:
  - 1. Change in activity time between pre and post intervention periods
    - a. Calculate this separately for PCAM vs. satellites
      - i. PCAM: pre intervention (2/10/16-2/9/17) vs. post intervention (3/10/17-10/10/17)
      - ii. Satellites: pre intervention (2/10/16-2/9/17) vs. post intervention (7/10/17-10/10/17)
    - Change in activity time between PCAM (intervention group) and satellites (control group) during first intervention period (3/10/17-6/9/17)
    - 3. Change in **total treatment time** between pre and post intervention periods
      - a. Calculate this separately for PCAM vs. satellites
        - i. PCAM: pre intervention (2/10/16-2/9/17) vs. post intervention (3/10/17-10/10/17)
        - ii. Satellites: pre intervention (2/10/16-2/9/17) vs. post intervention (7/10/17-10/10/17)
    - Change in total treatment time between PCAM (intervention group) and satellites (control group) during first intervention period (3/10/17-6/9/17)

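### Image rate and the two treatment-time outcomes get only unadjusted contrasts in the SAP, none of which handles both site and calendar time

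*SAP*

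**What the plan says.** SAP Outcome measures 4.b and 4.c make image rate a secondary outcome and treatment time an exploratory one. Their analyses sit in Analysis Plan section 2, headed "Unadjusted Analysis". Two kinds of contrast are listed.

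- **Within group.** For image rate: "Change in rate of images per total fractions taken pre and post intervention in each arm with 95% CI and p values". The windows are "PCAM: pre intervention (2/10/16-2/9/17) vs. post intervention (3/10/17-10/10/17" and "Satellites: pre intervention (2/10/16-6/9/17) vs. post intervention (7/10/17-10/10/17". Section 2.c uses the same PCAM windows for both times, but ends the satellite pre-period on 2/9/17 rather than 6/9/17.
- **Between sites.** For image rate: "Change in rate of images per total fractions between PCAM (intervention group) and satellites (control group) during first intervention period (3/10/17-6/9/17". For activity time: "Change in activity time between PCAM (intervention group) and satellites (control group) during first intervention period (3/10/17-6/9/17". Total treatment time has the same form. Only the first-period dates are given.

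Intervals and p-values are requested for the within-group image-rate change and for all the time comparisons.

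Adjustment for intervention, attending, location and time comes in section 3. Item 3.e there reads "Unadjusted and adjusted analyses for covariates in relation to primary outcome (daily IGRT use". The SAP Methods describe a logit-link GEE whose reported estimate is a difference in the percentage of patients with daily IGRT. The model in Protocol section 9 is likewise for binary daily imaging. Cost has its own regression model in 2.d; image rate and the two times have none.

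**The concern.** The trial has a year of baseline in both groups and a staggered start, so a comparison can be adjusted for site and calendar time together. The listed contrasts for these three outcomes do not do this. The site comparison carries any standing difference between PCAM and the satellites in imaging habits, equipment, set-up workflow or case mix. The before/after comparisons carry any drift over the year. Protocol 4.3 itself says that "the total number of palliative courses and associated daily IGRT varies across our main site and satellites".

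At stake are the estimates for fewer images and less time on the table. Protocol 11.6.2 names both as indirect benefits. A standing difference or a drift could hide an effect on them or create one.

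**Working it through.** The documents give no SD, effect size or power for these three outcomes, so there is no plan figure to reproduce. The check has four steps.

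**1. Windows (SAP 2.b, 2.c), in months from 2/10/16**

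| Window | Months | Midpoint |
|---|---|---|
| PCAM pre | 0–12 | 6 |
| PCAM post | 13–20 | 16.5 |
| Satellites pre, image rate | 0–16 | 8 |
| Satellites pre, times | 0–12 | 6 |
| Satellites post | 17–20 | 18.5 |
| First period, both groups | 13–16 | 14.5 |

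**2. What each contrast estimates.** Let the mean be G (PCAM only) + b × month + d (once treated).

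- PCAM vs satellites, first period: (G + 14.5b + d) − 14.5b = d + G
- PCAM pre/post: (G + 16.5b + d) − (G + 6b) = d + 10.5b
- Satellites pre/post, image rate: (18.5b + d) − 8b = d + 10.5b
- Satellites pre/post, times: (18.5b + d) − 6b = d + 12.5b
- For comparison, the first-period difference less the 12-month baseline difference: (d + G) − G = d

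The site contrast handles time but not site. The pre/post contrasts handle site but not time. For image rate the listed contrasts give two distinct equations in three unknowns. Subtracting one group's pre/post change from the other's does not help: it gives 0 for image rate and −2b for the times, because both groups are treated in their post windows.

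**3. Is G likely to be zero?** Protocol Table 2 gives a related measure, daily IGRT.

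- Satellites: (33 + 31 + 42 + 42)/(56 + 39 + 55 + 52) = 148/202 = 73.3%. PCAM: 81.4% of 623. Gap: 8.1 points.
- SE = √(0.814 × 0.186/623 + 0.733 × 0.267/202) = 0.0348, so the 95% CI is about 1.3 to 15.0 points, ignoring clustering.
- Without Pennsylvania Hospital (33/56), the satellites are 115/146 = 78.8% and the gap is 2.6 points.
- The table includes SBRT courses, which the trial excludes. Table 1 has 21, all daily. Removing them gives a gap of about 7.5 points if all were at PCAM (486/602 = 80.7%) and 11.2 if all were at the satellites (127/181 = 70.2%).

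**4. What a gap or drift would do (illustration on the daily-IGRT scale).** With G = 8.1, a true −20 points (the 0.2 in the protocol's power statement) appears as −11.9, and a true 0 as +8.1. With no effect and an assumed drift of −0.5 to −1 point a month, pre/post changes are −5.25 to −10.5 over 10.5 months and −6.25 to −12.5 over 12.5 months.

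Carrying the gap over to image rate needs an assumption. Suppose daily courses are imaged at every fraction and other courses at a share r, so that rate = p + r(1 − p).

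- r = 0.2 in both groups: 0.851 vs 0.786, gap 0.065. A 20-point fall at PCAM is worth 0.8 × 0.20 = 0.160 and would appear as 0.095.
- r = 0.2 at PCAM, 0.4 at satellites: 0.851 vs 0.840, gap 0.011, about 7% of 0.160.
- r = 0.2 at PCAM, 0.5 at satellites: 0.851 vs 0.866, gap −0.015, so the bias changes sign.

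The documents do not give r. For minutes they give no baseline at all.

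**The case against.** Several objections have force.

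- **A change between sites may mean a difference in change from baseline.** That is possible. But each pre/post item lists two windows, and each between-site item lists one and no estimator. At best the text is ambiguous.
- **Items 3.a to 3.c name no outcome, so the adjusted model might cover these three.** It is true that no sentence restricts it, and the SAP is still a commented working text. But 3.e, the logit link and the percentage estimate all point to daily IGRT, and a logit model does not suit minutes or a continuous rate.
- **For the two times, the planned windows already contain the answer.** This stands. Section 2.c uses the same 12-month baseline and the same first period in both groups, so a difference-in-differences point estimate follows by arithmetic. What is missing is its designation as the analysis, with an interval. For image rate this holds less directly, because the satellite pre-period runs to 6/9/17 and so contains the first period.
- **These outcomes are secondary and exploratory.** This also stands.

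A reader might infer more than the documents support. One inference is that the effect cannot be separated from site or time at all, or that the trial ignores its staggered design. The limit lies in the listed contrasts, not the data, and the primary analysis does use the design. Another is that the first-period contrast is mostly a site comparison. Even the r = 0.2 illustration has a gap of 0.065 against an effect of 0.160. A third is that 41% of the effect on image rate would be lost. That figure is only 8.1/20. It comes from a different outcome, in a table for August 2015 to August 2016 that includes excluded courses, and it moves with the assumed r.

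**Conclusion.** The point holds for one secondary and two exploratory outcomes. Followed as written, the SAP would give results for image rate, activity time and total treatment time from contrasts that each leave either site or calendar time uncontrolled. Daily IGRT has its own adjusted model and is unaffected.

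Table 2 makes a standing site difference plausible but does not measure it for these outcomes. The size and direction of bias in image rate and in minutes are therefore unknown. The algebra assumes additive site, time and intervention effects and a time trend common to both groups. The monthly drifts and values of r are illustrations. This should be corrected, but it does not threaten the trial's main result.

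**What to change.** In SAP 2.b and 2.c, make the inferential analysis for each of the three outcomes a single identity-link GEE with the main model's terms: intervention received, calendar month and site, clustered on attending. Fit it to all baseline and study months, leaving out each group's roll-out month (PCAM 2/10–3/9/17, satellites 6/10–7/9/17). Label the raw pre/post and first-period contrasts descriptive, and reconcile the two satellite pre-period end dates used for them.

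State the assumptions: a common time trend in the two groups and, with one intervention term, one effect across groups and periods. With only two groups allocated, the model cannot remove a trend specific to one group.

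The cost is SAP wording and three extra model fits on data the SAP already plans to use. The interval should be somewhat wider than for the raw contrast; by how much cannot be worked out, because no SDs are given. Trial conduct does not change.
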